Safety assessments will consist of monitoring and recording focused toxicities/adverse events (AE) and serious adverse events (SAE) unexpected to HCT (table 8), the regular monitoring of hematology, blood chemistry and urine values, vital signs, ECOG/Karnofsky performance status, and the regular physical examinations and EKG assessments as specified in the protocol.

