To date the main adverse events reported are similar among all the studies performed with oral PANO formulations. Information about common side effects already known about the investigational drug can be found in the Investigators' Brochure (IB) or will be communicated between IB updates in the form of Investigator Notifications. This information will be included in the patient informed consent and should be discussed with the patient during the study as needed.

- 7.2.1. The most common non-hematological events (Table 1) reported were:
 - 7.2.1.1. GI events (nausea/vomiting/ diarrhea);
 - 7.2.1.2. Fatigue and electrolytes abnormalities are less common.
- 7.2.2. The most common hematological toxicity reported was thrombocytopenia and to a lesser extent mild anemia and leukopenia.

These potential adverse effects will be monitored, and their occurrence recorded as specified in section 9.2. No specific diagnostic or therapeutic measures are prescribed by this protocol for majority of toxicities unless specified. GI toxicity is a common side effect of HCT especially in the immediate transplant period (see expected HCT complications section 9). Etiology of GI symptoms could be multifactorial including conditioning

regimen, medications, GVHD and/or infections. For patients with diarrhea, evaluations for other etiologies including infection are highly recommended. Endoscopy with biopsies should be considered for evaluation of GVHD if the patient is beyond day +22, but is left to the discretion of the treating physician.

8. Reasons to hold/discontinue treatment:

- 8.1. Investigator(s) decision to withdraw patient from the study in the event of inter-recurrent illness, adverse events, or other reason that he deems necessary to discontinue study drug. Patients who discontinue from the study for AE or SAE will all be evaluable. Date of and reason for study discontinuation will be noted. Patients whose treatment is interrupted or permanently discontinued due to an AE must be followed until resolution or stabilization of the event, whichever comes first.
- 8.2. Abnormal laboratory result unable to be corrected to levels acceptable for treatment with the study drug.
- 8.3. Patient non-compliance
- 8.4. Subject withdrew consent from study at any time for any reason.
- 8.5. Death.
- 8.6. Prolongation of QTcF (see section 5.6).

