9.1. AE definition: An adverse event (AE) is the appearance or worsening of any undesirable sign, symptom, or medical condition occurring after starting PANO that is unexpected with HCT. Table 8 describes criteria for “expected” toxicities for HCT/GVHD-related symptoms that are commonly observed in transplant patients. Certain Grade 4 toxicities under particular categories in the NCI CTCAE are common in the HCT transplant setting, and patients with Grade III or IV GVHD are likely to experience additional serious symptoms. These listed toxicities are likely related either to the HCT or preparatory and treatment regimens, however, the investigator must use best medical judgment in making an assessment as whether or not the study drug (PANO) may have had a contributory role.

Table 8. Expected Transplant/GVHD-Related Toxicities in HSC Transplant Patients.

Category	Symptoms/Event	Category	Symptom/Event
Dermatological	Pruritus Rash/dermatitis associated with high-dose chemotherapy or GVHD	Renal/Genitourinary	Bladder spasms/cystitis Creatinine elevation/renal failure Dysuria frequency-urgency Urinary retention
Constitutional	Fever, Rigors, Chills Headache Tremors Weight lost and gain Confusion due to medications Peripheral edema	Reproductive	Persistent amenorrhea
Gastrointestinal	Gastritis GERD Colitis Dehydration Diarrhea Nausea/vomiting Dysphagia Stomatitis/pharyngitis Hematocheza/melena Abdominal pain or cramping	Metabolic/Laboratory	Acidosis/alkalosis Amylase/lipase elevation Hypo-/Hyperglycemia Hypo-/Hyperkalemia Hypo-/hypercalcemia Hypo-/Hypermagnesium, Hypophosphatemia Hypo-/Hypernatremia Hypertriglyceridemia/Hyperlipidemia/hypercholesterolemia Hyperuricemia Increased LDH

Category	Symptoms/Event	Category	Symptom/Event
Hepatic	LFT elevation Bilirubin elevation Hypoalbuminemia Hepatomegaly	BMTComplex/ Multicomponent Events	GVHD* Stem-cell infusion complications Venoocclusive Disease/ascites
Cardio-vascular	Edema Hypertension/Hypotension Sinus tachycardia Arrhythmia (Atrial fibrillation/flutter; Sinus ventricular tachycardia and others) Vascular access complication- deep vein thrombosis requiring anticoagulation Thomboembolic event	Hematologic	Cytopenias Catheter associated venous thrombosis
Infections*	Bacterial, fungal and/or viral infections Sepsis/confusion		

*Infection and GVHD: These toxicities will not be considered AEs but data will be captured on eCRFs. Other toxicities will NOT be captured as expected HCT complications.

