Toxicity will be assessed using the NIH-NCI Common Terminology Criteria for Adverse Events, version(CTCAE) version 4.0 (v.4) (http://evs.nci.nih.gov/ftp1/CTCAE/CTCAE_4.03_2010-06-14_QuickReference_5x7.pdf).

9.2. AE reporting:

- 9.2.1. All non-hematological toxicities unexpected with HCT will be reported from the first day PANO is administered until day 180±7 days unless specified otherwise in the protocol. After day 180±7 post HCT subjects will only be followed only for GVHD, relapse and survival until day 365±30.
- 9.2.2. Information about relevant AE unexpected to HCT, whether volunteered by the subject, discovered by investigator questioning, or detected through physical examination, laboratory test or other means, will be collected and recorded. AE should be followed as

appropriate for at least 14 days following the last dose of PANO. All AE should be treated appropriately. Such treatment may include changes in study drug treatment including possible interruption or discontinuation, starting or stopping concomitant treatments, changes in the frequency or nature of assessments, hospitalization, or any other medically required intervention.

- 9.2.3. As far as “possible or definitive” related AE unexpected to HCT, each adverse event should be evaluated to determine:
 - 9.2.3.1. the severity grade (mild, moderate, severe) or (grade 1-4)
 - 9.2.3.2. its relationship to the study drug(s) (suspected/not suspected)
 - 9.2.3.3. its duration (start and end dates or if continuing at final exam)
 - 9.2.3.4. action taken (no action taken; study drug dosage adjusted/temporarily interrupted; study drug permanently discontinued due to this adverse event; concomitant medication taken; non-drug therapy given; hospitalization/prolonged hospitalization)
 - 9.2.3.5. whether it constitutes a serious adverse event (SAE).

- 9.3. **SAE is an undesirable sign**, symptom or medical condition which:
 - 9.3.1. Is fatal or life-threatening
 - 9.3.2. Results in persistent or significant disability/incapacity
 - 9.3.3. Constitutes a congenital anomaly/birth defect
 - 9.3.4. Is medically significant, i.e., defined as an event that jeopardizes the patient or may require medical or surgical intervention to prevent one of the outcomes listed above
 - 9.3.5. Requires inpatient hospitalization or prolongation of existing hospitalization
 - 9.3.6. Note that hospitalizations for the following reasons should not be reported as serious adverse events:

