 - 9.3.6.1. Routine treatment or monitoring of the studied indication, not associated with any deterioration in condition
 - 9.3.6.2. Elective or pre-planned treatment for a pre-existing condition that is unrelated to the indication under study and has not worsened since signing the informed consent
 - 9.3.6.3. Social reasons and respite care in the absence of any deterioration in the patient’s general condition
 - 9.3.6.4. Note that treatment on an emergency outpatient basis that does not result in hospital admission and involves an event not fulfilling any of the definitions of a SAE given above is not a serious adverse event
 - 9.3.7. Reporting: See section 11.7.

9.4. Special considerations for AE attribution:

- 9.4.1. Diarrhea:
 - 9.4.1.1. From PANO first dose to day +21 post-HCT attribution to study drug is difficult as majority of patients develop diarrhea as part of the conditioning regimen and/or rarely due to GVHD.
 - 9.4.1.2. After day + 22 post HCT, if a patient develops diarrhea grade 3 (increase more than 7 stools above baseline) or grade 4 (life threatening), excluding infection and/or GVHD, the AE is considered “probable” or “definitive” related to PANO. Protocol specific stopping rules have been formulated for excess GI toxicity (section 12.2).
- 9.4.2. Vomiting:
 - 9.4.2.1. From PANO first dose to day +21 post-HCT attribution to study drug is difficult as vomiting is a possible complication of the conditioning regimen and/or rarely due to GVHD.
 - 9.4.2.2. After day + 22 post HCT if a patient develops vomiting grade 3 (increase more than 6 episodes in 24 hours) or grade 4 (life threatening), excluding infection and/or GVHD, it is considered “probable” or “definitive” related to PANO. Protocol specific stopping rules have been formulated for excess GI toxicity (section 12.2).

10. Required Evaluations: Evaluations and study visits are listed in Appendix C.

- 10.1. Demographics:** Ethnic origin, date of birth, gender, primary diagnosis necessitating HCT, HLA-A, B, C, DRB1 matching of donor and recipient, stem cell product (peripheral blood stem cells are only allowed), Date of HCT.
- 10.2. Physical examination:** A directed examination will be performed as per treating physician discretion and based upon patient symptoms. Performance status will be specified by Karnofsky (Appendix D). Comorbidity score (Appendix E).

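### Cytopenias are named as panobinostat effects but excluded from adverse-event capture, and no result is planned on post-engraftment count falls, dose holds or exposure

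*Combined protocol and SAP*

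**What the plan says.** Section 7.2 gives thrombocytopenia as the most common hematologic toxicity of PANO, with anemia and leukopenia less prominent, and then states: "These potential adverse effects will be monitored, and their occurrence recorded as specified in section 9.2".

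The recording rules are in section 9:
- 9.1 confines adverse events to those not expected after transplant. Table 8 lists cytopenias as expected, without limit by grade, day or engraftment status.
- The Table 8 footnote sends infection and GVHD to the eCRF and says of the rest: "Other toxicities will NOT be captured as expected HCT complications".
- 9.2.1 sets the reporting scope to day 180±7: "All non-hematological toxicities unexpected with HCT will be reported".
- 9.2.2 follows adverse events as "appropriate for at least 14 days following the last dose of PANO".
- 9.2.3.4 has an action-taken field that includes "study drug dosage adjusted/temporarily interrupted", but only for events not expected after transplant.

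Section 8.12 acts on blood counts after engraftment. PANO is held at ANC <500/uL or platelets <20,000/uL, and a second fall leads to every-other-week dosing. Section 7 names "the regular monitoring of hematology, blood chemistry and urine values" among the safety assessments. Section 12.5 has one sentence on adverse events and nothing on blood counts, holds or doses taken.

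**The concern.** Leaving out the aplasia caused by conditioning is sensible, since every patient has it. The difficulty is that the exclusion does not stop at engraftment, although 8.12 treats a later fall as a reason to hold the drug. Diarrhea and vomiting are also expected in Table 8, yet 9.4 gives each a late rule, beginning for diarrhea "After day + 22 post HCT, if a patient develops diarrhea grade 3". Cytopenias have dosing consequences but no matching rule.

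Section 1.11 says patients will be evaluated for safety, and 3.1 says the result should show whether PANO merits randomized testing. Section 1.4 also hopes to learn whether PANO has fewer toxic effects than vorinostat. In the vorinostat prophylaxis trial described in 1.3, post-engraftment thrombocytopenia was the most common hematologic grade 3-4 event (n=9 of 50 patients, or 18% if each event is one patient). This trial plans no corresponding figure, nor any count of how often PANO was held or halved in frequency for low counts.

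**Working it through.** No stated figure in the plan bears on this point, so the check is mainly a comparison of sections.

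**1. Is there a recording route?** Section 7.2 sends the hematologic effects to 9.2. Section 9.2.1 admits only non-hematological events, and 9.2.2 and 9.2.3 admit only events not expected after transplant, which Table 8 says cytopenias are not. The clause in 9.2.1 that allows for other provisions does not help, because 7.2 points back to 9.2.

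**2. Does another section fill the gap?**
- 9.1 asks the investigator to judge whether PANO contributed to a listed toxicity. No recording step follows.
- 5.7.3.4 and 10.12.2 keep doses and dose changes, but not a reason for a hold. Section 8.1 covers permanent stopping: "Date of and reason for study discontinuation will be noted". Dose dates alone do not identify a count-driven hold, because PANO is also held for QTcF (5.6), early toxicity (8.8), GI symptoms (8.9) and mucositis (Appendix G).
- 11.7.1 sends every SAE to the drug supplier. An asymptomatic low count need not be an SAE, and no SAE rate is planned.
- 8.10.2 keeps later low counts out of delayed engraftment, and 12.2 counts only toxicity not expected after transplant.

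**3. How much of the schedule is affected?** 26 × 7 = 182 days. Treatment starts s = 5 or 6 days before transplant (Appendix G), and median engraftment in earlier trials was day d = 14 (platelets) or 16 (WBC) (8.10.2). Share after engraftment = (182 − s − d)/182:
- d = 14: 163/182 = 89.6% and 162/182 = 89.0%
- d = 16: 161/182 = 88.5% and 160/182 = 87.9%

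This is a share of the schedule, not of missed events.

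**4. When should capture end?** Repeating the Appendix G weekly pattern to week 26 puts the last dose at day 174 (busulfan/fludarabine, start day −6), day 175 (busulfan/fludarabine, start day −5; fludarabine/melphalan with Wednesday, Friday or Sunday start) or day 176 (fludarabine/melphalan with Thursday or Saturday start). Adding 14 days gives day 188-190. One made-up week of 3 doses gives day 195-197. Both are later than day 180+7 = 187.

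**5. What could a table show?** Exact (Clopper-Pearson) 95% intervals, assuming 36-44 engrafted patients:
- 0/36: 0-9.7%; 0/40: 0-8.8%; 0/44: 0-8.0%
- 4/40 (10%): 2.8-23.7%
- 0/15, if the trial stops after stage 1: 0-21.8%

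**6. Background ranking.** At 20 mg, four times this dose (Table 2 in 1.5, N=309), the leading grade 3-4 events were thrombocytopenia 66 (21.4%), neutropenia 42 (13.6%) and anaemia 29 (9.4%), with fatigue next at 13 (4.2%).

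**The case against.** The strongest reply is that this is a deliberate exclusion with most of the information kept elsewhere. Section 7.2 leaves the scope to 9.2, so recording only what 9.2 specifies can be called consistent. Section 8.10.2 says that later low counts also come from infection and other complications, which a single arm cannot separate from PANO. Doses are recorded, the 8.12 triggers are numeric, and 10.4 requires laboratory results to be reviewed before dosing, so many holds could be reconstructed. Serious consequences go to SAE forms, infections go to eCRFs, and non-relapse mortality is an endpoint. Safety is not a listed objective. The centre's own study in acute GVHD (1.4) called hematologic toxicity mild, with return to baseline in 1-2 weeks.

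Much of this stands, and it limits the point. A reader might infer that the trial keeps no information on cytopenias, that patients are unprotected, or that the stopping rule is wrong. The documents support none of these: the 8.12 holds protect patients, and 12.2 is explicitly built on toxicity not expected after transplant. Nor do the 20 mg rates predict the rate at 5 mg.

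What does not stand is that retained raw records amount to a result. Reconstruction afterwards has to guess among several hold reasons, and nothing commits the trial to a tabulation. The reassuring study gave 4 weeks of dosing; this one gives 26. If 7.2 does defer wholly to 9.2, its statement that these effects are recorded has no content for cytopenias.

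**Conclusion.** The point holds in a limited form. Followed exactly, the plan yields no planned result on post-engraftment count falls, count-driven holds, every-other-week restarts or exposure, although cytopenia is the leading severe toxicity in the protocol's own background data. Only the tolerability conclusion is affected.

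The size cannot be given as a number of missed events, because the rate at 5 mg after transplant is unknown. The exposed share of the schedule, 88-90%, assumes the full 26 weeks and the historical engraftment medians. The intervals assume 36-44 engrafted patients and one outcome per patient.

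A further tempting step is to count every grade 3-4 cytopenia after engraftment. That would overstate toxicity. Section 8.10.1 declares engraftment at ANC >500/uL and platelets >20,000/uL, and patients just above those limits may still be recovering from conditioning. This assumes that such counts still fall in grade 3-4; the protocol cites CTCAE but does not reproduce its cut-offs. The trigger therefore has to be a new fall or a worsening after recovery. With that trigger, the change is a worthwhile cheap improvement rather than a correction on which the trial depends.

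**What to change.** 1. **Table 8 footnote and 9.2.1.** Add an exception: a new fall after primary engraftment (8.10.1) to the 8.12 thresholds, ANC <500/uL or platelets <20,000/uL, is captured until day 180 or 14 days after the last PANO dose, whichever is later. Other CTCAE grade 3-4 cytopenias are captured only if new or worsened after counts had recovered above that grade.
2. **Hold reason.** Record the reason for each temporary PANO hold.
3. **Section 12.5.** Add one descriptive table, in engrafted patients who received PANO, giving these events, the proportion with a first hold under 8.12, the numbers of holds and of every-other-week restarts, and the proportion of planned doses taken by day 100 and overall.

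The primary analysis, dosing rules and stopping rule stay as they are. The cost is one CRF field, modest entry of counts, one table, and an amendment reviewed by the drug supplier and the IRB (11.5). Two limits remain. Ascertainment depends on how often counts are drawn in care (Appendix C, as it can be read here, shows no blood-count row). Attribution to PANO in a single arm stays limited, so the table should be presented as description.

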- 3.3. **Sample Size and accrual rate.** It is estimated that 2 patients will be entered into the treatment study each month, therefore, we anticipate 24 months for completion of the study that will require **n=44** total patients for the treatment arm. We are planning to enroll **n=20** patients for “external control patients”. We anticipate 0.5 patients/month for “external control” subjects and accrual will happen concomitant to treatment arm patients. Therefore a total of **64** subjects will be accrued in total including treatment arm and external control.
- 3.4. **Patient Follow up.** Patients will be evaluated weekly from day of transplant until day 100 to measure acute GVHD using standard scoring system (defined in Appendix A). Stage of GVHD will be assessed for each site of involvement (e.g. skin, liver, and gut), as well as a composite score for overall acute GVHD grade determined. Pathologic confirmation of aGVHD will be dictated by usual clinical practice. Patient will be followed on days +90 +/-14, 120 +/- 14, 150 +/- 14, 180+/- 14, 270+/-30, and 360 +/- 30 for chronic-GVHD assessment and adverse events toxicity assessment. Taper of immunosuppression is suggested- not mandatory and treatment of GVHD is not mandated (section 6.2-6.3).
- 3.5. **Withdrawal.** from the study will take place under the following circumstances: those patients who sign consent for the study, but fail to initiate treatment due to:
- 3.5.1. denial of coverage from insurance provider
 - 3.5.2. disease progression prior to initiation of treatment
 - 3.5.3. death prior to initiation of treatment
 - 3.5.4. withdrawal of patient consent at any time after therapy

4. Patient Population: Inclusion and Exclusion criteria

- 4.1. **Inclusion Criteria:**
- 4.1.1. Male or female

- 4.1.2. Age \geq 18 years or older at time of enrollment
 - 4.1.3. Signed informed consent
 - 4.1.4. Hematologic disorder requiring allogeneic hematopoietic cell transplantation
 - 4.1.5. LVEF \geq 45% by MUGA scan or echocardiogram
 - 4.1.6. FEV1, FVC, and DLCO adjusted \geq 50% of predicted values on pulmonary function tests
 - 4.1.7. Transaminases (AST, ALT) $<$ 3 times upper limit of normal values
 - 4.1.8. Creatinine clearance calculated \geq 50mL/min
 - 4.1.9. Karnofsky Performance Status Score \geq 60%.
 - 4.1.10. HLA matched 8/8 (A, B, C, DRB1) related or unrelated donor
- 4.2. **Exclusion Criteria:**
- 4.2.1. Active infection not controlled with appropriate antimicrobial therapy

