- 10.12.1. GVHD: Date of onset of acute GVHD, names of immunosuppressive drugs received and dates, Date of onset of chronic GVHD, Organ staging will be assessed prior to therapeutic intervention, according to the consensus grading⁴⁴ (Appendix A). The diagnosis of Grades II-IV GVHD should be confirmed by histo-pathological examination whenever possible but is not mandatory. Pathology will be reviewed by H. Lee Moffitt Cancer Center pathologists.
 - 10.12.2. Study medications: Records of study medication used, dosages administered, and intervals between visits will be recorded during the study. Drug accountability will be noted by research pharmacy.
 - 10.12.3. AE: Significant findings made after the start of study drug which meet the definition of an AE and SAE must be recorded.
 - 10.12.4. Infections and relapse will be captured but they are not considered AE
- 10.13. Correlative studies.** See appendix F

11. Data and Safety monitoring:

The Data Safety & Monitoring Plan (DSMP) will ensure that this trial is well designed, responsibly managed, appropriately reported, and that it protects the rights and welfare of patients. The following internal and external review and monitoring processes provide oversight and active monitoring of this trial:

- The Principal Investigators (PI)
- The Scientific Review Committee (SRC)
- The Protocol Review and Monitoring Committee (PRMC);
- The Research Compliance Division (RCD) of the Cancer Center's Compliance Office;
- The Institutional Review Board.
- We will follow the Moffitt Cancer Center policy for monitoring of Investigator Initiated Trials (MRI-P.PSO.03)

The protocol includes a section that specifies the following with respect to Adverse Event (AE) reporting: what constitutes an AE (versus what is a serious adverse event), the entities to which AE should be reported, the timing of this reporting, and the person or persons responsible for reporting. This includes prompt (within one day of knowledge of the event) reporting to the IRB for unanticipated risks to subjects and reporting in writing within five working days to the IRB. It is required reporting of SAE to Novartis but not AEs as indicated in section 9. If necessary, corrective action and/or educational programs will occur to ensure subject safety and data integrity. Reports to the SRC, PMC, and IRB will be submitted as required.

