11.7. Instructions for data reporting

- 11.7.1. To ensure patient safety, every SAE, regardless of suspected causality, occurring after the patient has provided informed consent and until at least 14 days after the patient has stopped study treatment must be reported to Novartis within 24 hours of learning of its occurrence.

Any SAEs experienced after this 14 days period should only be reported to Novartis if the investigator suspects a causal relationship to the study treatment. Recurrent episodes, complications, or progression of the initial SAE must be

reported as follow-up to the original episode within 24 hours of the investigator receiving the follow-up information. An SAE occurring at a different time interval or otherwise considered completely unrelated to a previously reported one should be reported separately as a new event.

Information about all SAEs is collected and recorded on the Serious Adverse Event Report Form as outlined per contractual agreement; all applicable sections of the form must be completed in order to provide a clinically thorough report. The investigator must assess and record the relationship of each SAE to each specific study treatment (if there is more than one study treatment), complete the SAE Report Form in English, and send the completed, signed form by fax within 24 hours to the oncology Novartis Drug Safety and Epidemiology (DS&E) department.

The telephone and telefax number of the contact persons in the local department of Drug Safety and Epidemiology (DS&E) are included in the contractual agreement. The original copy of the SAE Report Form and the fax confirmation sheet should be kept with the case report form documentation at the study site.

Follow-up information is sent to the same contact(s) to whom the original SAE Report Form was sent, using a new SAE Report Form stating that this is a follow-up to the previously reported SAE and giving the date of the original report. Each re-occurrence, complication, or progression of the original event should be reported as a follow-up to that event regardless of when it occurs. The follow-up information should describe whether the event has resolved or continues, if and how it was treated, whether the blind was broken or not, and whether the patient continued or withdrew from study participation.

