12.2. Stopping criteria for toxicity

A patient who receives at least one dose of the study drug (PANO) per protocol is evaluable for toxicity. As shown in Table 9, the accrual will be suspended if c or more of n patients experience CTCAE (v.4) grade 3 or higher toxicity unexpected with transplant, where n is the number of evaluable patients and c is the number of patients who experience CTCAE (v.4) grade 3 unexpected toxicity or higher. Assuming true toxicity rate is 20% and the type I error rate is 5%, the stopping boundary was computed by Ivanova et al⁴⁹. If true toxicity rate is 20%, 40% and 50%, then the probability of early stopping is 4.9%, 79% and 98%, respectively.

Table 9. Boundary for early stopping rule for toxicity

n	3	4	5	6	7	8	9	10	11	12
c	3	4	4	5	5	5	6	6	6	6
n	21	22	23	24	25	26	27	28	29	30
c	9	10	10	10	11	11	11	11	12	12

Note: 1. n = # of patients who receive at least one dose of study drug

2. c = # of patients who experience CTCAE (v4) Grade 3 or higher toxicity unexpected to HCT

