Appendix G.

Panobinostat administration as per conditioning regimen. Patients will be treated with PANO 5 MG PO TIW (3 doses about 48 hours apart in a 7 day period) QW for 26 weeks starting prior to stem cell infusion. During the study, PANO will be administered orally as once daily dose. Patients should receive their once-a-day oral dose of PANO approximately at the same time each day in AM. Each dose of PANO should be taken with about 8 oz / 240 ml glass of water. Patients should be instructed to swallow the capsules whole and not chew them. Patients must avoid grapefruit or grapefruit juice and seville (sour) oranges during the entire study. If the patient forgets to take his/her dose on scheduled treatment day or cannot take it due to mucositis and/or HCT related GI toxicities (nausea/vomit), then he/she should take PANO on that same day within 16 hours after the missed dose if possible. After more than 16 hours, that day's dose should be withheld, and the patient should wait to take PANO until the next scheduled treatment day (i.e., patients should be instructed not to try to make-up the missed dose after 16 hours). If mucositis and/or GI toxicity preclude PANO oral intake, patient are allowed to hold up to 3 doses and administration should be resumed once mucositis and/or toxicity resolves. Patient should complete missed doses and then continue treatment as planned per protocol extending PANO administration period.

Busulfan and Fludarabine Chemotherapy

Sunday	Monday	Tuesday	Wed	Thursday	Friday	Saturday
-5 BU FLU PANO(1)	-4 BU FLU	-3 BU FLU PANO(2)	-2 BU FLU	-1 PANO(3)	0	+1
+2	+3 PANO	+4	+6 PANO	+7	+8 PANO	

Sunday	Monday	Tuesday	Wed	Thursday	Friday	Saturday
			-6 BU FLU PANO(1)	-5 BU FLU	-4 BU FLU PANO(2)	-3 BU FLU
-2 PANO(3)	-1	0	+1 PANO	+2	+3 PANO	+4
+5	+6 PANO	+7	+8 PANO		+10 PANO	

Fludarabine and Melphalan Chemotherapy

Sunday	Monday	Tuesday	Wed	Thursday	Friday	Saturday
			-5 FLU/MEL PANO	-4 FLU/MEL	-3 FLU/MEL PANO	-2 FLU/MEL
-1 Rest PANO	0	+1	+2 PANO	+3	+4 PANO	+5
+6	+7 PANO	+8	+9 PANO	+10	+11 PANO	+12
Sunday	Monday	Tuesday	Wed	Thursday	Friday	Saturday
				-5 FLU/MEL PANO	-4 FLU/MEL	-3 FLU/MEL PANO
-2 FLU/MEL	-1 Rest PANO	0	+1	+2	+3 PANO	+4
+5	+6 PANO	+7	+8 PANO	+9	+10 PANO	+11
Sunday	Monday	Tuesday	Wed	Thursday	Friday	Saturday
					-5 FLU/MEL PANO	-4 FLU/MEL
-3 FLU/MEL PANO	-2 FLU/MEL	-1 Rest PANO	0	+1	+2 PANO	+3
+4	+5 PANO	+6	+7 PANO	+8	+9 PANO	+10

Fludarabine and Melphalan Chemotherapy

Sunday	Monday	Tuesday	Wed	Thursday	Friday	Saturday

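### Section 9.2.1 closes AE reporting at day 180±7, against Section 3.4 and Appendix C, and does not tie the cut-off to the last panobinostat dose

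*Combined protocol and SAP*

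**What the plan says.** Section 9.2.1 states that non-hematological toxicities not expected with transplant "will be reported from the first day PANO is administered until day 180±7 days unless specified otherwise in the protocol". Its last sentence then reads: "After day 180±7 post HCT subjects will only be followed only for GVHD, relapse and survival until day 365±30". The exception for other sections stands only in the first of these sentences.

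Other parts of the protocol bear on the same period:

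- Section 3.4 lists visits on days "180+/- 14, 270+/-30, and 360 +/- 30 for chronic-GVHD assessment and adverse events toxicity assessment".
- Appendix C marks the AE and SAE row in all eight columns from +28 to +365, including +270 and +365. The +180 column has a window of ±14 days.
- Section 9.2.2 asks that AEs be followed as "appropriate for at least 14 days following the last dose of PANO".
- Section 10.12.3 gives no end date: "Significant findings made after the start of study drug which meet the definition of an AE and SAE must be recorded".
- Section 11.7.1 covers every SAE from consent "until at least 14 days after the patient has stopped study treatment must be reported to Novartis within 24 hours", and later SAEs if a causal link is suspected.
- Section 12.2 sets the toxicity rule: "the accrual will be suspended if c or more of n patients experience CTCAE (v.4) grade 3 or higher toxicity unexpected with transplant". It states no time limit.
- Appendix G says that, for mucositis or GI toxicity, "patient are allowed to hold up to 3 doses and administration should be resumed once mucositis and/or toxicity resolves". It adds that missed doses are completed and the dosing period is extended.

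**The concern.** Staff cannot both assess adverse events at day 270 and follow patients only for GVHD, relapse and survival. One coordinator may close AE reporting at day 180±7 under 9.2.1 while another keeps recording under 3.4 and Appendix C. Non-serious toxicity on or soon after the last doses would then be captured for some patients and not for others.

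The cut-off is a transplant day, while the risk follows the drug. Treatment lasts 26 weeks, so the last doses come close to the cut-off, and a made-up hold pushes them closer or past its nominal day.

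What is at stake is the completeness of late safety data and even counting under 12.2. Section 3.3 plans accrual over 24 months, so the first patients pass day 187 while that rule is still running.

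**Working it through.** **The texts side by side.** For +270 and +360/+365, 9.2.1 says GVHD, relapse and survival only, while 3.4 and Appendix C say AE assessment. This is a direct contradiction. Section 9.2.2 speaks of following AEs, which can mean events already identified, and 10.12.3 is silent on an end date. Neither contradicts 9.2.1, but neither supplies a matching end date.

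**Inputs for the calendar check.**

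- Doses: three a week for 26 weeks (5.7.1.3, Appendix G), so 26 × 3 = 78.
- First doses: the seven distinct Appendix G grids, each continued Monday/Wednesday/Friday. Where a printed day label skips, the weekday column is used.
- 9.2.1 window: 180 − 7 = 173 to 180 + 7 = 187.
- Day-180 visit window in 3.4 and Appendix C: 180 − 14 = 166 to 180 + 14 = 194.

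**Last dose with no hold.**

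| Grid (first dose) | Doses before regular weeks | Remaining | Day of dose 78 |
|---|---|---|---|
| BU/FLU, Sunday −5 | 3 | 75 = 25×3 | 7 + 24×7 = 175 |
| BU/FLU, Wednesday −6 | 5 | 73 = 24×3 + 1 | 6 + 24×7 = 174 |
| FLU/MEL, Wednesday −5 | 5 | 73 = 24×3 + 1 | 7 + 24×7 = 175 |
| FLU/MEL, Thursday −5 | 4 | 74 = 24×3 + 2 | 8 + 24×7 = 176 |
| FLU/MEL, Friday −5 | 4 | 74 = 24×3 + 2 | 7 + 24×7 = 175 |
| FLU/MEL, Saturday −5 | 6 | 72 = 24×3 | 15 + 23×7 = 176 |
| FLU/MEL, Sunday −5 | 3 | 75 = 25×3 | 7 + 24×7 = 175 |

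Dose 78 therefore falls on +174 (one grid), +175 (four) or +176 (two).

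**With holds made up at the end.** Each 3-dose hold moves dose 78 by 7 days.

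| Case | Dose 78 | Last dose + 14 | Days past 187 | Doses after 173 | Doses after 180 | Doses after 187 |
|---|---|---|---|---|---|---|
| No hold | +174 to +176 | +188 to +190 | 1–3 | 1–2 | 0 | 0 |
| One 3-dose hold | +181 to +183 | +195 to +197 | 8–10 | 4–5 | 1–2 | 0 |
| Two 3-dose holds (assumed) | +188 to +190 | +202 to +204 | 15–17 | 7–8 | 4–5 | 1–2 |

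The two-hold row assumes that the Appendix G allowance applies per episode, which the text does not state.

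**Cross-check.** Counting 26 strict calendar weeks instead of 78 doses, the last dose is −6 + 25×7 + 4 = 173 or −5 + 25×7 + 4 = 174. Adding 14 days gives 187 or 188, so without a hold the overrun past day 187 is then 0–1 day.

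**The case against.** The strongest defence is that 9.2.1 defers to the rest of the protocol, and that 3.4, Appendix C and 8.1 do specify otherwise (8.1 follows AEs that interrupt or stop treatment until they resolve or stabilize). On that view the last sentence is a drafting slip. This does not settle the matter. The deferral is absent from the sentence that limits follow-up, and if 3.4 and Appendix C override it, the day-180 limit has little effect. The wording needs repair either way.

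Other parts of the defence stand:

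- On schedule, every dose precedes day 180, and after one made-up 3-dose hold every dose still precedes day 187.
- For patients who stop early, for instance because of GVHD, a fixed date gives longer reporting than last dose + 14 days. The remedy therefore has to take the later of the two.
- No calculation shows that a missed event would change a Table 9 decision.

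A reader might also infer more than the text supports:

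- That 9.2.2 and 10.12.3 contradict 9.2.1 as well. The first can mean known events, and the second only lacks an end date.
- That patients will routinely be dosed after reporting has ended. Dosing after day 187 needs repeated or longer made-up holds. Appendix B, which has doses missed around QT-prolonging drugs given later, could contribute, but the documents give no frequency.
- That serious late toxicity would be lost. Section 11.7.1 covers it.

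**Conclusion.** The point holds as an internal inconsistency of minor severity. Section 9.2.1 contradicts 3.4 and Appendix C on AE assessment at +270 and +360/+365, and its cut-off can fall during dosing or within 14 days of the last dose. For patients who complete treatment, last dose + 14 days passes day 187 by 1–3 days with no hold and by 8–10 days after one made-up 3-dose hold.

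The gap concerns non-serious unexpected toxicity only. Such events of grade 3 or higher feed the 12.2 rule, so counting should be the same for all patients. The primary endpoint and the two-stage rule are unaffected.

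The day counts assume 78 doses, Monday/Wednesday/Friday continuation beyond the weeks that Appendix G prints, and held doses added at the end. The contradiction itself rests on none of these.

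**What to change.** Amend 9.2.1 in three ways:

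1. Report all unexpected AEs through day 187 or 14 days after the last PANO dose, whichever is later. This gives a definite closing day and removes the ±7 against ±14 mismatch.
2. State that grade 3 or higher unexpected toxicity in that window counts in the 12.2 rule.
3. Reword the last sentence: after that window, patients are followed for GVHD, relapse and survival. At the +270 and +365 visits, the AE/SAE assessment of 3.4 and Appendix C records ongoing events and any new event suspected to be related to PANO.

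This works whether or not doses held for low counts under 8.11–8.12 are made up, so those sections need no change for this purpose.

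The cost is one wording amendment and a few more days of reporting per patient: 1–3 days past day 187 with no hold, 8–10 after one. Dose, planned visits and patient numbers stay the same. A phone or chart check may be needed when the window closes after the day-180 visit. After one hold it closes at +195 to +197, beyond that visit's last allowed day of +194, and the next visit window opens only at 270 − 30 = day 240.
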